Randomization and blinding

[name] will oversee the allocation of the participants to the control or treatment group and will be the only researcher who will not be blinded as to the experimental condition to which each participant belongs.

Participants will be allocated to the control or treatment group according to a pre-generated sequence of pseudorandom numbers, although deviations from this sequence may be made in order to ensure that the two groups are approximately matched in severity of symptoms. After prism adaptation training [name] will give the participant the set of goggles that they will be using for their sham/real prism adaptation treatment. The goggles will be handed to the participant in a sealed, opaque bag so that none of the other researchers will be able to see what kind of goggles the participant has been given. The participant will be instructed to seal the goggles in the same bag when they bring them back to the Dartmouth Hitchcock Medical Centre at the end of the treatment period. [name] will not be involved in any of the pre- or post-treatment assessments. In order to gauge progress an initial analysis will be performed once 60% of the participants have completed the post-treatment assessment, in which case the other researchers will be unblinded as to the group membership of the participants who have already completed the main components of the study. Aside from [name], the remaining members of the research team will be blind as to the group membership of the remaining 40% of participants.

Prism adaptation

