Patients will undergo self-guided adaptation sessions in their own home, after initial training in the adaptation procedure by [name]. Patients in the experimental condition will receive goggles fitted with prismatic lenses that induce a 15° upward shift in the visual image. Patients in the control condition will receive goggles fitted with neutral lenses. For each prism/sham adaptation session, patients will sit in a chair within reaching distance of a wall or cabinet upon which two dime-sized targets will be placed (one above the other, approximately ten inches apart). While wearing the goggles, patients will point rapidly to one target then the next, bringing their hand back to their torso between each pointing movement. They will be instructed to perform these movements ‘as quickly as possible’ for a total of 50 pointing movements (<5 minutes) in each treatment session. After performing 50 pointing movements the will remove the goggles. Each patient will undergo two daily sessions of prism adaptation for 14 consecutive days.

Assessment of Posture and Gait

Assessments of posture, gait, and activities of daily living will be performed by a Neurologist and a trained Physical Therapist at the Dartmouth-Hitchcock Medical Center on two occasions immediately before and immediately after the intervention period (the pre- and post-test). Three categories of outcome measures will be used; standard clinical assessments, mechanized measurements, and self-report questionnaires will be conducted by mail and/or phone on three further occasions (one week, one month and three months post treatment).

1) Standard clinical assessments.

Four commonly used clinician-scored evaluations will be used.

General Neurological Examination. This will be performed by a trained neurologist, and involves simple sensory and motor tests.

The Unified Parkinson’s Disease Rating Scale (motor component). Several dimensions of motor control are assessed by a clinician-scored evaluation. Patients are asked to perform simple tasks such as tapping their fingers as quickly as possible for five seconds, and their performance on each item is scored on a scale of 0 (“normal”) to 4 (“can barely perform the task”). The total score out of 92 is computed.

Timed Up and Go test. Starting from a seated position, the person is required to stand up, walk to a line 10 meters away, turn around, walk back and sit down. The person is timed.

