All data will be anonymized and analyzed using non-parametric and parametric standard tests using SPSS software. Statistical analyses will be performed with appropriate correction for multiple comparisons.

The endpoints will be the post-treatment clinical assessment session.

Scores for each of the outcome measured will be analyzed using two-by-two, repeated measures ANOVAs, with Group (sham, prism) and session (pre, post) as independent factors. In the case of the self-report measures, two-by-four repeated measures ANOVAs will be performed with Group (sham, prism) and session (pre, post, one-month, three-months) as independent factors. Post hoc analyses will be in the form of t-tests (or non-parametric equivalents), corrected for multiple comparisons. These tests will determine if prism adaptation improves performance to a greater extent than sham treatment. In addition, 95% confidence intervals will be constructed around mean performance for each group before and after sham or prism treatment to test whether the group performance deviates significantly from established normative data or diagnostic cut-offs (e.g., for the UPDRS).

5. Study Progress Monitoring

Note: appropriate monitoring may include periodic assessment of the following:

- data quality
- timelines
- recruitment and enrollment

Provide a description of the methods which will be used to determine the progress of the study, including periodic assessments of data quality, timelines, recruitment, and enrollment as appropriate:

We will check into using the psychiatry DSMB.

6. Risks & Benefits

Note: Risks may be physical, psychological, social, legal, economic, to reputation, or others.

a. Describe any potential risks, their likelihood and seriousness:

There is a minor risk that the treatment or assessment procedures will result in some fatigue or discomfort. This is expected to be short-lived, and would be no greater than that involved in patients' normal physical therapy. To minimize the risk of fatigue during the pre- and post-treatment assessments, patients will be provided with breaks between tasks as required. Prism adaptation has been used for studying sensory-motor integration in healthy individuals for over a century, and in the treatment of stroke patients with hemispatial neglect for over ten years. In this time there have been no reports of serious adverse effects.

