Yes, the study is based on the premise that a link between a genotype or a biomarker and a specific disease or condition is clinically useful in predicting the development of that specific disease or condition. **Please complete the [Genetic Research Form](#) and upload it to the ‘Supporting Documents’ page in Rapport.**

-OR -

Yes, the study is looking for an association between a genotype or a biomarker and a specific disease or condition, but at this point it is not clear if the genetic marker has predictive value. The uncertainty regarding the predictive value of the genetic marker is such that studies in this category will not involve referral of participants to genetic counseling; however, participants will be informed of genetic testing in the consent form. **Please comment:**

10. Equitable Participant Selection

a. Estimated number of participants at Dartmouth CPHS reviewed sites:

Approximately 30 patients will be enrolled in the study at Dartmouth-Hitchcock Medical Center.

b. Provide a justification of the proposed sample size

For the methods specified above, there is no well-established method for calculation of group size as yet. We can, however, draw on experience from previous experiments, indicating what is the minimal/optimal number of participants for detecting significant effects. Previous studies that tested the effects of a similar prism adaptation treatment protocol on sensory and motor problems in stroke patients have used between 12 and 16 patients per group (Frassinetti, Serino). We aim to approach 40 patients with at least 32 completing the study (16 per group), which will provide a sufficient dataset even if up to 20% of participant withdraw before the completion of the study

c. Define the target population:

The patient population that will be targeted are the patient is referred for Parkinson's disease with gait impairment at Dartmouth-Hitchcock Medical Center

Inclusion/Exclusion Criteria:

Inclusion

- Diagnosis of idiopathic Parkinson's Disease
- Referral for gait training
- Aged 40-85
- If the subject is taking CNS-acting CNS-acting medications (benzodiazepines, hypnotics, antidepressants), regimen must be stable for 30 days prior to baseline visit
- Subjects with Stage II.5 – Stage IV (Hoehn and Yahr scale) where stage II.5 is bilateral involvement with axial involvement, but without balance difficulty, to Stage IV where one has severe disability but is still able to walk or stand unassisted.

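### The random sequence may be overridden to match the groups on severity, with no measure, trigger, cap, random element or log; a concealed rule-based scheme would give the balance without the discretion

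*Combined protocol and SAP*

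**What the plan says.** Section 3, Randomization and blinding, takes assignments from a pre-generated sequence of pseudorandom numbers and then states that "deviations from this sequence may be made in order to ensure that the two groups are approximately matched in severity of symptoms". One researcher oversees allocation and "will be the only researcher who will not be blinded as to the experimental condition".

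The same section contains three further relevant statements:

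- Goggles are passed over inside packaging that cannot be seen through, "so that none of the other researchers will be able to see what kind of goggles the participant has been given".
- The allocating researcher "will not be involved in any of the pre- or post-treatment assessments".
- Once 60% of participants have completed the post-treatment assessment, an initial analysis is run and the other researchers learn the arms of those participants.

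Under Prism adaptation, patients treat themselves at home "after initial training in the adaptation procedure by" a researcher whose name has been removed. Section 12a makes the PI the only person who obtains consent. Section 4 analyses each outcome by a repeated-measures ANOVA "with Group (sham, prism) and session (pre, post) as independent factors", with no severity term.

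**The concern.** To match groups by overriding a sequence, someone must know the incoming patient's severity, the next assignment and the current make-up of the groups. Judgement then acts at the moment of assignment, which is the step that randomisation is meant to take out of anyone's hands. The bag and the allocator's absence from assessments protect blinding after assignment. They do not stop the next assignment from being known and changed.

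At stake is whether a reader of the results can verify that assignment was independent of prognosis. If deviations respond only to severity, the comparison is sound. If they also respond to something else that predicts outcome (fitness, motivation, likely adherence), it is not. The plan has no rule, limit or record by which to tell these cases apart.

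Enrolment is protected only in part. With names removed, it cannot be read whether the PI who obtains consent is also the allocator. After the 60% analysis the other researchers know past assignments, and together with a habit of matching on severity this could make later assignments easier to guess.

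**Working it through.** **Inputs.** Section 10b aims for 40 patients approached and 32 completing, 16 per group, allowing 20% withdrawal: 32 / (1 − 0.20) = 40, so that arithmetic reproduces. Sections 3 and 10a give about 30 patients instead, so results at other sizes are noted below. There is no power calculation to reproduce; Section 10b says "there is no well-established method for calculation of group size as yet". The following are assumptions, not document values: the outcome is pre-to-post change with SD 1; prognosis, or severity, explains R² = 10% to 50% of its variance; tests are two-sided at 5%.

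**Case A: deviations only to balance severity.** Simulation at 32 patients. From the 7th patient on, an assignment is overridden when it would leave a severity gap above a trigger, the other arm is closer, and arm sizes stay within 3 of each other. With triggers of 0.2, 0.3 and 0.5 SD, about 14%, 10% and 5% of assignments are overridden. Bias is below 0.01 SD at each trigger.

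**Case B: a fraction q of assignments tracks other prognosis.** Better-prognosis patients go to prism and worse to sham.

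- Prognosis gap = 2 × q × √(2/π): 0.160 SD at q = 0.1 and 0.319 SD at q = 0.2.
- Bias = gap × √R².
- Standard error = √(2/16) = 0.354 SD.
- Type I error from the noncentral t with 30 degrees of freedom and noncentrality bias / 0.354.

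| q | R² | Bias (SD) | Type I error |
|---|---|---|---|
| 0.1 | 0.1 | 0.050 | 5.2% |
| 0.1 | 0.3 | 0.087 | 5.7% |
| 0.1 | 0.5 | 0.113 | 6.1% |
| 0.2 | 0.1 | 0.101 | 5.9% |
| 0.2 | 0.3 | 0.175 | 7.7% |
| 0.2 | 0.5 | 0.226 | 9.5% |

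About half of these assignments would agree with the sequence anyway, so q = 0.1 to 0.2 means 1.6 to 3.2 actual switches among 32. The last row becomes 9.2% at 15 per group and 10.7% at 20 per group.

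**Balance under each scheme, 32 patients.**

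| Scheme | Mean absolute severity gap (SD) |
|---|---|
| Sequence alone, 16 per group | √(4/32) × √(2/π) = 0.28 |
| Overrides, triggers 0.2 / 0.3 / 0.5 SD | 0.10 / 0.13 / 0.19 |
| Permuted blocks, two strata, median split | 0.18 |
| Permuted blocks, two strata, 80/20 split | 0.21 |
| Minimisation on the score, assignment probability 0.8 | 0.10 |

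With the sequence alone, the chance of a gap above 0.5 SD is 15.7%. With blocks it is about 2.5% for a median split and about 6% for an 80/20 split.

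**Why the analysis must follow the allocation.** Balancing on severity and then testing without a severity term is conservative. Unadjusted type I error is 1.8% to 4.2% with median-split blocks and 1.1% to 4.2% with minimisation. With the same factor in the model it is 4.8% to 5.0% and 5.1%. This comes from the missing term, not from the deviations. In the Section 4 ANOVA the test of interest is group by session. A severity main effect does not alter that test; a severity-by-session term does.

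**The case against.** The strongest reply is that Section 3 authorises deviations for one purpose, matching severity, and that this purpose produces no meaningful bias (Case A). Every positive bias figure assumes conduct that the protocol does not permit. The allocator is also kept out of the assessments, so may know little about prognosis beyond severity, and an R² of 50% for two-week change is only an assumption. All of this stands, which is why Case B is an illustration and not an estimate.

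A second reply is that severity balance is worth having at this size and that frequent overrides achieve it more tightly than a single stratum. That also stands; minimisation on the score matches the overrides without the discretion.

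A reader might go further and infer that assignments will be steered, that the trial is not randomised, or that the allocator recruits patients. The documents support none of these. The base sequence is pseudorandom, so the missing random element concerns only the deviations. With names removed, it cannot be shown that the allocator obtains consent or gives the training, or even that the allocator personally decides each deviation. The opposite inference, that blinding of everyone else secures enrolment, is also too strong, because that blinding lapses for completed participants at the 60% analysis.

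**Conclusion.** The point holds as a cheap improvement. The permission to deviate is explicit, and no section supplies a measure, trigger, cap, random element or log. Used only as stated, it costs essentially nothing in bias. What it removes is the means to prevent, or later detect, any other use. The actual size is unknown. The illustrative range of 0.05 to 0.23 SD and 5.2% to 9.5% rests on 16 per group, R² of 10% to 50%, and 10% to 20% of assignments tracking prognosis in one direction. It is neither a forecast nor a worst case.

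**What to change.** Delete the permission to deviate and use a pre-programmed, concealed scheme with no overrides, in one of two forms:

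- permuted blocks of varying size, stratified by one pre-specified severity factor already collected at entry (for example Hoehn and Yahr stage or UPDRS motor score), with the cut-point fixed in advance; or
- minimisation on the baseline severity score with a random element.

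Record severity before the assignment is released and log every assignment. Keep the sequence and block sizes from those who enrol or assess, including after the 60% analysis. The existing unblinded allocator may run the scheme and hand over the goggles.

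Include the same severity factor in the analysis of each outcome with its session interaction or, equivalently for the two-session outcomes, as a covariate in a model of change or of the post-treatment score. Where the factor is the baseline of the outcome itself, as UPDRS motor score would be for the UPDRS outcome, use ANCOVA on the post-treatment score.

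If deviations have already been made, list each one (sequence assignment, actual assignment, reason), report the number, and add a sensitivity analysis by sequence assignment.

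Cost: a short script or sealed stratified lists, and about one degree of freedom. One coarse stratum balances less tightly than frequent overrides (0.18 to 0.21 SD against 0.10 to 0.13 SD). Minimisation closes that gap but needs a program at each assignment and is partly predictable to anyone who knows the current group make-up.

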We previously tested the hypothesis that adaptation to upward-shifting prisms, producing a downward recalibration in pointing, would reduce forward stepping time in patients with Parkinson's disease. The rationale for this approach was that, based on the results of Tilikete and colleagues, adaptation to upward-shifting prisms would shift the standing posture forwards. In a study of 16 patients we found that a single five-minute session of prism adaptation reduced forward stepping time by an average of 183ms (~10% reduction) [4]. Backward stepping time was unchanged, and a test of adaptation to downward-shifting prisms with control participants showed no effect on forward or backward stepping. This study provides proof-of-concept that prism adaptation can reduce forward stepping time in patients with Parkinson's disease using a laboratory-based measure of stepping.

2. Objectives and Hypotheses

Objective: To compare the effect of two weeks of twice-daily adaptation to upward prismatic shifts in the visual field vs. two weeks of sham adaptation on measures of posture and gait in patients with idiopathic Parkinson's Disease.

Hypotheses: Compared to patients who undergo sham prism adaptation, patients who complete two weeks of real prism adaptation therapy will show reduced stepping initiation times, greater displacement of the body over the feet during stepping initiation, and increased self-report of confidence while walking. We will also measure a number of other common clinical indicators to determine whether prism adaptation improves motor performance and postural responses to external perturbations.

3. Study Design

Describe all study procedures, materials, and methods of data collection:

The study will have a longitudinal, repeated-measures, between-subjects, double-blind, sham-controlled design. Thirty patients with idiopathic Parkinson's Disease will be randomly assigned to undergo two weeks of twice-daily sessions of adaptation to upward-shifting prisms, or sham adaptation (in which patients perform the same sensory-motor task while wearing goggles fitted with neutral lenses). Measures of posture and gait (see below) will be recorded in two sessions: pre- and post-treatment. Additional long-term follow-up will be obtained through questionnaires by mail at one week, one month and three months post-treatment. The timeline for the research sessions, intervention period and follow-up questionnaires are outlined in Figure 1.

Procedures:

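### At the 60% look, nothing keeps the assessors from learning completed patients' groups and the interim trend before they rate the last 40%, whose own allocation stays masked

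*Combined protocol and SAP*

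**What the plan says.** Section 3 calls the design double-blind and names one unblinded researcher, who allocates patients, hands over the goggles in a sealed opaque bag and takes no part in the assessments. Under Randomization and blinding it then plans one exception: "In order to gauge progress an initial analysis will be performed once 60% of the participants have completed the post-treatment assessment". At that point "the other researchers will be unblinded as to the group membership of the participants who have already completed the main components of the study". The protection kept for later patients is that, apart from the allocator, "the remaining members of the research team will be blind as to the group membership of the remaining 40% of participants".

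The pre- and post-treatment assessments "will be performed by a Neurologist and a trained Physical Therapist". They include the UPDRS motor section and the Functional Gait Assessment, both scored by a clinician. Section 4 analyses each outcome in a two-by-two ANOVA with group and session (pre, post) as factors, and sets the endpoint at the post-treatment session.

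Questionnaires continue after that session. The opening of section 3 has them sent by mail. The assessment subsection has them "conducted by mail and/or phone on three further occasions (one week, one month and three months post treatment". Section 4 puts the one-month and three-month scores into a two-by-four ANOVA. Section 5, on monitoring, says only that use of a DSMB will be looked into.

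**The concern.** The stated protection covers one kind of knowledge, which group a later patient is in. It does not cover what the look itself reveals. The neurologist and physical therapist are not expressly listed among the researchers to be unblinded, but nothing exempts them, and the only person kept out of the assessments is the allocator. On the text, they may learn two things before rating the rest: which of the patients they examined wore prisms, and which group is ahead.

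That matters for scales that depend on a clinician's judgement. An assessor who has just matched remembered remarks or behaviour to true groups is better placed to guess the group of the next patient, and knows what result to expect. The documents make some cues plausible. Prisms shift the image 15° upward and the sham lenses do not. At the second visit patients also rate adverse effects, enjoyment and perceived change, and no text says who is kept from those answers.

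The stated purpose of the look does not require assessors to know any of this.

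**Working it through.** **1. Which number the 60% refers to.** Section 10 gives at least 32 completers with up to 20% withdrawing: 32 / (1 − 0.20) = 40, which reproduces the plan's 40 approached. Section 1 also says 40 are allocated, but section 3 says 30 and section 10 puts enrolment at about 30. The look is therefore sized for all three values.

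**2. Patients rated after the look, with no delay.** Last 40% = 0.4 × N:
- 0.4 × 40 = 16
- 0.4 × 32 = 12.8, about 13
- 0.4 × 30 = 12

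**3. Effect of a delay.** Knowledge arrives at unblinding, not when the 60% mark is reached, so the figures in step 2 are maxima. The plan gives neither accrual nor delay. Assume post-treatment visits spread evenly over T = 12 months and unblinding L months after the 60% mark. Visits still to come = 0.4N − (N/T) × L.

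| N | L = 0 | L = 1 | L = 2 | L = 3 |
|---|---|---|---|---|
| 40 | 16 | 12.7 | 9.3 | 6 |
| 32 | 12.8 | 10.1 | 7.5 | 4.8 |
| 30 | 12 | 9.5 | 7.0 | 4.5 |

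For example, 16 − (40/12) × 1 = 12.7.

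**4. What limits the bias.** Suppose an assessor guesses a patient's group correctly with probability g, and scores patients guessed as prism higher by d, in the direction of improvement, than those guessed as sham. In patients rated after the look the group difference shifts by gd − (1 − g)d = (2g − 1)d. If both groups have the same share of late patients, the shift in the whole trial is at most 0.4 × (2g − 1)d. At g = 0.5 it is zero: leniency or severity applied equally to both groups drops out of the group-by-session comparison. Neither g nor d can be taken from the documents, so no size of bias is claimed.

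**5. Which outcomes are exposed.** The section 2 hypotheses name stepping initiation time, displacement of the body over the feet, and self-reported walking confidence. The UPDRS motor section and Functional Gait Assessment fall under the further sentence "We will also measure a number of other common clinical indicators to determine whether prism adaptation improves motor performance". Displacement is read from a force-plate report and is less open to judgement. For the first 60%, all endpoint-session data exist before unblinding.

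**6. Why follow-up cannot be counted.** On the same even-spread assumption, patients still owing the three-month form at unblinding = (N/T) × max(0, min(0.6T, 3 − L)). For N = 40 and L = 0:
- T = 6: (40/6) × min(3.6, 3) = 20
- T = 12: (40/12) × 3 = 10
- T = 24: (40/24) × 3 = 5

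With L = 3 the result is 0 for every T. If all follow-up is by mail, or no unblinded person telephones, the number exposed is 0 whatever T and L are. A range of 0 to 20 that turns on three unstated facts (accrual, delay, caller) is not a usable estimate.

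**The case against.** The best case for the plan is that the exception is declared openly and that the part of the blind that matters most is kept. Later patients' groups stay masked and their goggles travel in a sealed bag. A rater who knows only the trend cannot favour a group without guessing who is in it. The team already has a directional expectation, because section 1 reports its own 16-patient study with stepping about 183 ms faster, so an interim trend may add little. The clinician-scored scales are also not those named in the hypotheses.

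All of that stands, and it keeps the point small. It does not close the gap. Prior belief is not the same as being told the true groups of patients one has personally examined, which is what could improve a guess. Declaring the exception also does not explain why assessors need group data in order to gauge progress.

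Three stronger readings are tempting and are not supported.
- A reader might infer that the blind is broken for the last 40%. The text keeps their individual allocation masked.
- A reader might infer that endpoint data for the first 60% are compromised. Those data are recorded before unblinding.
- A reader might infer an inflated type I error. If success could be declared at either look at an assumed unadjusted two-sided 0.05, the overall error would be about 0.080 (correlation √0.6 between looks). But the plan attaches no efficacy test or claim to the look and states no alpha, so this is not a finding.

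**Conclusion.** The point holds as a cheap improvement. Under the current wording, assessors may know completed patients' groups and the interim trend while rating at most 16 of 40, about 13 of 32, or 12 of 30 patients on judgement-based scales. The number falls as unblinding is delayed. This rests on reading the neurologist and physical therapist as among those unblinded, which the text permits and does not state. Bias arises only so far as a patient's group can be guessed, and its size cannot be estimated from the documents.

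Follow-up is a secondary risk and may be nil. A reader might infer that unblinding contaminates the later questionnaires. That would need the undefined term for the main parts of the study to mean the post-treatment visit, follow-up by telephone, a caller who is unblinded, and an effect of the call on the patient's own answers. The plan unblinds researchers, not patients, and does not say who would call.

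The absence of a stated decision after the look, the undefined term and the mail/telephone mismatch are missing detail and would not carry the point alone.

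**What to change.** In section 3, Randomization and blinding, replace the unblinding of the other researchers with wording such as:

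> Assessors will remain blind to individual group membership and to group-level interim results until the last post-treatment assessment is complete. Anyone who telephones participants for follow-up will remain blind to both until the last three-month questionnaire is complete. The 60% look will review recruitment, completion and data quality on pooled data. If any part is done by group, it will be seen only by existing team members with no assessment, allocation or follow-up-contact role, or by the DSMB if one is used. The look serves only to gauge progress and carries no efficacy claim. Safety review is not affected.

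The allocator is kept away from by-group results because the plan lets allocation depart from the random list: "deviations from this sequence may be made in order to ensure that the two groups are approximately matched in severity of symptoms". Assessors with no follow-up role need not wait for the three-month forms, since their last rating is the final post-treatment visit.

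The cost is protocol wording and a decision on who, if anyone, sees results by group. Assessors would see group results later than now planned. In a small team nobody may be free of all three roles; if there is also no DSMB, the look would have to be pooled only and the planned by-group analysis would wait until the end.
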